Appendix 9 Algorithm for the Evaluation of Progressive Multifocal Leukoencephalopathy

Appendix 10

Clinical Criteria for Diagnosing Anaphylaxis

These criteria are taken from a summary report from the second symposium on the definition and management of anaphylaxis, conducted by the National Institute of Allergy and Infectious Disease/Food Allergy and Anaphylaxis Network.¹ Anaphylaxis is highly likely when any one of the following three criteria is fulfilled:

1. Acute onset of an illness (minutes to several hours) with involvement of the skin, mucosal tissue, or both (e.g., generalized hives, pruritus or flushing, swollen lips-tongue-uvula)

AND AT LEAST ONE OF THE FOLLOWING:

- Respiratory compromise (e.g., dyspnea, wheeze-bronchospasm, stridor, reduced peak expiratory flow, hypoxemia)
 - Reduced blood pressure or associated symptoms of end-organ dysfunction (e.g., hypotonia, syncope, incontinence)
2. Two or more of the following that occur rapidly after exposure to a likely allergen for that patient (minutes to several hours):
 - Involvement of the skin-mucosal tissue (e.g., generalized hives, itch-flush, swollen lips-tongue-uvula)
 - Respiratory compromise (e.g., dyspnea, wheeze-bronchospasm, stridor, reduced peak expiratory flow, hypoxemia)
 - Reduced blood pressure or associated symptoms (e.g., hypotonia, syncope, incontinence)
 - Persistent gastrointestinal symptoms (e.g., crampy abdominal pain, vomiting)
 3. Reduced blood pressure after exposure to known allergen for that patient (minutes to several hours):
 - Infants and children: low systolic blood pressure (age specific)² or greater than 30% decrease in systolic blood pressure
 - Adults: systolic blood pressure of less than 90 mmHg or greater than 30% decrease from that person's baseline

¹ Sampson HA, Muñoz-Furlong A, Campbell RL, et al. Second symposium on the definition and management of anaphylaxis: summary report—second National Institute of Allergy and Infectious Disease/Food Allergy and Anaphylaxis Network symposium. *J Allergy Clin Immunol* 2006;117:391–7.

² Low systolic blood pressure for children is defined as less than 70 mmHg from 1 month to 1 year, less than (70 mmHg + [2 x age]) from 1 to 10 years, and less than 90 mmHg from 11 to 17 years.

Appendix 11 Simple Endoscopic Score for Crohn's Disease (SES-CD)

Table 1 Definitions of Simple Endoscopic Score for Crohn's Disease

Variable	Simple Endoscopic Score for Crohn's Disease values			
	0	1	2	3
Size of ulcers	None	Aphthous ulcers (Ø 0.1 to 0.5 cm)	Large ulcers (Ø 0.5 to 2 cm)	Very large ulcers (Ø > 2 cm)
Ulcerated surface	None	< 10%	10–30%	> 30%
Affected surface	Unaffected segment	< 50%	50–75%	> 75%
Presence of narrowings	None	Single, can be passed	Multiple, can be passed	Cannot be passed

Ø, Diameter.

Table 2 Example of SES-CD scoring form

	Ileum	Right colon	Transverse colon	Left colon	Rectum	Total
Presence and size of ulcers (0–3)						
Extent of ulcerated surface (0–3)						
Extent of affected surface (0–3)						
Presence and type of narrowings (0–3)						
SES-CD =						

Adapted from: Daperno M, D'Haens G, Van Assche G, et al. Development and validation of a new, simplified endoscopic activity score for Crohn's disease: the SES-CD. *Gastrointestinal Endoscopy* 2004;60:505–512.

4.2.4	Open-Label Extension Timeframe	23
4.3	INTERIM ANALYSES	23
4.4	CHANGES TO PROTOCOL-PLANNED ANALYSES.....	23
5.	SUPPORTING DOCUMENTATION.....	23
6.	REFERENCES	24

LIST OF TABLES

Table 1	Key Characteristics of GA29145 OLE-SM in CD (Juniper)	9
Table 2	Efficacy Outcome Definitions	11
Table 3	Analysis Population.....	12

LIST OF FIGURES

Figure 1	Study Schema for Part 1 (Open-Label Extension; OLE) of the OLE-SM Study.....	8
Figure 2	Study Schema for Part 2 (Safety Monitoring; SM) of the OLE-SM Study	8

LIST OF ABBREVIATIONS AND DEFINITIONS OF TERMS

Abbreviation or Term	Description
5-ASAs	5-aminosalicylic acid
AE	adverse event
AEGT	Adverse Events Group Terms
AESI	adverse event of special interest
ALT	alanine aminotransferase
AP	abdominal pain
AST	aspartate aminotransferase
ATA	anti-therapeutic antibodies
BMI	body mass index
CCOD	clinical cutoff date
CD	Crohn's Disease
CDAI	Crohn's Disease Activity Index
CD-PRO/SS	Crohn's Disease- Patient Reported Outcome/ Signs and Symptoms
CMH	Cochran-Mantel-Haenszel
COVID-19	Coronavirus Disease 2019
CRP	C-reactive protein
CS	corticosteroids
CSR	Clinical Study Report
CTCAE	Common Terminology Criteria for Adverse Events
e-CRF	electronic Case Report Form
EQ-5D	EuroQL 5 Dimension Questionnaire
HLGT	High Level Group Terms
HLT	High Level Term
IBDQ	Inflammatory Bowel Disease Questionnaire
ICE	intercurrent event
iDMC	independent Data Monitoring Committee
IS	immunosuppressant
IxRS	interactive voice/Web based response system
LOCF	last-observation-carried-forward
MAR	missing at random
MedDRA	Medical Dictionary for Regulatory Activities
MI	multiple imputation
MICE	multivariate imputation by chained equations
mITT	modified intent to treat

MMRM	mixed models for repeated measures
NRI	non-responder imputation
OLE	open label extension
PD	pharmacodynamics
PK	pharmacokinetic
PML	progressive multifocal leukoencephalopathy
PRO2	patient-reported outcomes-2
PT	preferred term
Q4W	every 4 weeks
SAE	serious adverse event
SAP	statistical analysis plan
SC	Subcutaneous
SES-CD	simplified endoscopic score for Crohn's disease
SF	stool frequency
SM	safety monitoring
SOC	system organ class
TNF	tumor necrosis factor
TNF-IR	TNF-inadequate responder
ULN	upper limit of normal
WOCF	worst-observation-carried-forward

1. INTRODUCTION

The analyses described in this Statistical Analysis Plan (SAP) will supersede those specified in Protocol GA29145 for the purposes of reporting.

The purpose of this document is to describe the analyses for reporting out Part 1 of the Open-Label-Extension Safety Monitoring (OLE-SM) study for GA29145. This SAP will solely focus on reporting data collected during Part 1 (OLE) of GA29145.

This OLE-SM study is composed of two parts:

1. Part 1 is the OLE for eligible patients, during which etrolizumab, 105 mg SC, will be administered Q4W followed by a 12-week safety follow-up post-treatment.
2. Part 2 is the 92-week PML SM for all patients, during which no etrolizumab will be administered.

[figure not shown]
Patients who are enrolled in Part 1 (OLE) should participate in Part 2 (SM).

There may be patients from Study GA29144 who are ineligible for or choose not to participate in Part 1 (OLE) who will be asked to directly enroll in Part 2 (SM).

Key characteristics of the GA29145 OLE-SM are provided in [Table 1](#). Treatment arms and rollover of patients from induction/maintenance to GA29145 OLE-SM from parent CD studies are depicted in [Figure 1](#) and [Figure 2](#).

[figure not shown]
The maximum number of patients enrolled in GA29145 OLE-SM is approximately 1150 (i.e., all patients enrolled in Study GA29144). No formal sample size calculations were performed.

Figure 1 Study Schema for Part 1 (Open-Label Extension; OLE) of the OLE-SM Study

OLE=open-label extension; OLE-SM=open-label extension—safety monitoring; Q4W=every 4 weeks; Q12W=every 12 weeks; SC=subcutaneous.

Figure 2 Study Schema for Part 2 (Safety Monitoring; SM) of the OLE-SM Study

OLE=open-label extension; OLE-SM=open-label extension—safety monitoring; PML=progressive multifocal leukoencephalopathy; ~Q24W=approximately every 24 weeks.

Table 1 Key Characteristics of GA29145 OLE-SM in CD (Juniper)

Study	GA29145 (Phase III)	
Treatment (Number Exposed)	Open-label etrolizumab 105 mg SC Q4W (n= up to ~1150)	
Study Phases	OLE up to 10 years from FPI 12-week safety follow-up 92-week PML monitoring	
Key Eligibility Criteria	Part 1 (OLE)	Part 2 (SM)**
	
 • Previously enrolled in Study GA29144 • Starting at Week 10, CDAI > patient's baseline CDAI • Not eligible for maintenance* • A clinical relapse during the Maintenance Phase[^] • Complete the Maintenance Phase including the Week 66 or Week 74 	
 • Previously enrolled in Study GA29144 and are not eligible or chose not to enroll in Part 1 (OLE) and completed the 12-week SFU • Participated in Part 1 (OLE) and completed the 12-week SFU

CD= Crohn's disease; CDAI =Crohn's Disease Activity Index; FPI=first patient in; OLE=open- label extension; PML=progressive multifocal leukoencephalopathy; Q4W=every 4 weeks; SC=subcutaneous; SM=safety monitoring; SFU = safety follow-up.

*Including patients who completed the Week 14 visit in Study GA29144 and could not subsequently enter the Maintenance Phase, because the sample size was achieved and enrollment into the Maintenance Phase was closed.

**All patients must have completed the 12- week safety follow-up in either GA29144 or GA29145, Part 1 (OLE), as applicable, prior to entering Part 2 (SM).

[^] A clinical relapse during the Maintenance Phase of Study GA29144 is defined as meeting at least one of the following criteria on two consecutive visits (may include unscheduled visits), with at least one of the two consecutive CDAI scores \geq 220: CDAI score \geq the baseline (Week 0) score, or CDAI score \geq 100 points higher than the Week 14 score

Changes to the protocol-planned analyses are described in [Section 4.4](#).

1.1 OBJECTIVES AND ENDPOINTS

The objectives of this OLE-SM study are as follows:

Part 1 (OLE)

- To assess the long-term safety and efficacy of etrolizumab in patients eligible for Part 1 (OLE)

Part 2 (SM)

- PML safety monitoring in patients who have stopped study treatment

This SAP will only cover analyses for GA29145 Part 1 (OLE) objective.

Other Safety Objectives

- To evaluate the incidence, rate per subject-year, and severity of infection-related adverse events
- To evaluate the incidence and rate per subject-year of malignancies
- To evaluate the incidence and severity of hypersensitivity reactions

Exploratory Objectives

- To assess endoscopic appearance at Week 108

The following endpoint was de-prioritised as a safety objective to an exploratory objective from Protocol GA29145, version 6. Rationale for this is detailed in Section 4.4:

- To evaluate the incidence and the clinical significance of anti-therapeutic antibodies (ATAs)

1.2 STUDY DESIGN

Details of the Part 1 (OLE) study design can be found in the Protocol Synopsis section, Section 3 and Study Schema in Figure 1 of Protocol Version 6.

1.2.1 Protocol Synopsis

The Protocol Synopsis is in Protocol Synopsis Section of study GA29145 Protocol Version 6. For additional details, see the Schedule of Assessments in Appendices 1 and 2 of study GA29145 Protocol Version 6.

1.3 OUTCOME MEASURES FOR GA29145 PART 1 (OLE)

1.3.1 Efficacy Outcome Measures

The efficacy outcome measures for this study are as follows:

- Crohn's Disease Activity Index (CDAI) remission assessed at 12-week intervals during GA29145 Part 1 (OLE)
- Clinical remission assessed at 12-week intervals during GA29145 Part 1 (OLE), as defined by a stool frequency (SF) mean daily score ≤ 3 and an abdominal pain (AP) mean daily score ≤ 1 with no worsening in either subscore compared to baseline, averaged over 7 days prior to visit

- Simple Endoscopic Score for Crohn’s disease (SES-CD) score assessed at Week 108 or at early withdrawal, if prior to Week 108, during GA29145 Part 1 (OLE)

The efficacy outcome definitions are provided below.

Table 2 Efficacy Outcome Definitions

Outcome Term	Definition
CDAI	CDAI is a composite of eight assessments: number of liquid or soft stools, abdominal pain, general well-being, presence of complications, taking Lomotil (diphenoxylate/atropine) or other opiates for diarrhea, presence of an abdominal mass, hematocrit, and percentage deviation from standard weight
SES-CD	SES-CD is an endoscopic score derived from four variables (ulcers, ulcerated surface, inflamed surface, and presence of narrowing) that are scored in five ileocolonic segments.
CDAI Remission	CDAI Score < 150
Clinical Remission	An SF mean daily score ≤3 and an AP mean daily score ≤1 with no worsening in either subscore compared to baseline, where the average is taken over 7 days prior to visit

AP= abdominal pain; CDAI = Crohn’s Disease Activity Index; SES-CD= Simple Endoscopic Score for Crohn’s disease; SF = liquid/soft stool frequency.

1.3.2 Safety Outcome Measures

The safety outcome measures for GA29145 Part 1 (OLE) of this study are as follows:

- Incidence and severity of adverse events
- Incidence of serious adverse events
- Incidence, rate per subject-year, and severity of infection-related adverse events
- Incidence of serious infection-related adverse events
- Incidence and severity of injection-site reactions
- Incidence of adverse events leading to etrolizumab discontinuation
- Incidence of laboratory abnormalities
- Incidence and rate per subject-year of malignancies
- Incidence and severity of hypersensitivity reactions

1.3.3 Exploratory Outcome Measures

The exploratory outcome measures for GA29145 Part 1 (OLE) of this study are as follows:

- SES-CD ≤ 4 (≤ 2 for ileal patients), with no segment having a subcategory score (i.e., for ulceration size and extent, affected surface, or narrowing) that is > 1 , at Week 108
- Change in SES-CD score between Week 0 (Study GA29144) and Week 108 or early withdrawal (Study GA29145, Part 1; OLE)

Incidence of ATAs to etrolizumab (*de-prioritised from a safety outcome measure and will not be analysed or reported in primary Clinical Study Report [CSR] for GA29145 Part 1 (OLE). See Section 4.4 for details).*

1.4 ANALYSIS TIMING

GA29145 Part 1 (OLE) will be formally analyzed and reported in a primary CSR after the last patient has completed the 12-week safety follow up, following last dosing on 15th May 2022. Note that a database snapshot rather than a database lock for reporting Part 1 (OLE) of GA29145 will take place.

2. STATISTICAL HYPOTHESES AND SAMPLE SIZE DETERMINATION

2.1 STATISTICAL HYPOTHESES

Due to the non-comparative character of the study, no statistical tests or hypotheses are planned; all efficacy parameters will be summarized descriptively.

2.2 SAMPLE SIZE DETERMINATION

The maximum number of patients that could be enrolled into the GA29145 OLE-SM study is approximately 1150 (i.e., all patients enrolled in Study GA29144). No formal sample size calculations were performed.

3. ANALYSIS SETS

The analysis population for the purposes of analyses are presented in below:

Table 3 Analysis Population

Open-Label Extension	Patients who receive at least one dose of study drug in Study GA29145 Part 1 (OLE)
	Timeframe is from first dose of study drug in the GA29145 Part 1 (OLE) to the patient's last visit in GA29145 Part 1 (OLE), or safety follow-up, whichever is latest. Summaries will primarily focus on safety events arising after first dose of study drug in Study GA29145 Part 1 (OLE)

4. STATISTICAL ANALYSES

For reporting, a synoptic CSR will be reported. Due to this synoptic nature, limited efficacy data will be reported and all safety outcome measures will be reported in the CSR.

4.1 GENERAL CONSIDERATIONS

4.1.1 Analysis of Study Conduct

The number of patients who discontinued early (early discontinuation of OLE treatment or early termination from the study) or completed the study will be tabulated.

Reasons for early discontinuation of treatment or early termination from the study will be listed and summarized. Any eligibility criteria exceptions and other major protocol deviations will also be summarized.

Since Part 1 (OLE) of GA29145 was terminated by the Sponsor on 15th February 2022, no patients are expected to reach treatment completion. As a result of this, the end of Part 1 (OLE) of GA29145 is defined from the last dose date in GA29145 on 15th May 2022.

In summary, the following will be summarised for GA29145 Part 1 (OLE):

- Analysis populations
- Patient disposition
- Study treatment completion/discontinuation
- Study completion/discontinuation
- Major protocol deviations
- Exposure

Treatment Labels

For the OLE population, the only treatment arm to be summarized is:

Group	Patients Included
OLE Etrolizumab	Patients in the OLE population who receive at least one dose of etrolizumab in Study GA29145 Part 1 (OLE)

All tables should be presented by treatment group only.

Part 1 (OLE) Day 1

OLE Study Day 1 is defined as the day patient has the first receipt of study drug in GA29145 Part 1 (OLE).

Baseline

Baseline is defined as the last available assessment prior to first receipt of study drug in the Induction Phase of the parent study, GA29144.

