4.4.4 Description of Study Assessments in Part 1 (OLE)

Data from the final visit of Study GA29144 will be used for analysis and data sets for the first visit of the OLE-SM study. If any procedure and assessment was missed at the time of the final visit, it should be performed for the first visit of the OLE-SM study.

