4.2 SAFETY ANALYSES

Safety data will be assessed through descriptive summaries using the OLE population. All data available up until the clinical cut-off date (CCOD) will be reported.

Safety evaluations for the OLE population will include data from the first dose of treatment in Part 1 (OLE) until the patient completes/withdraws from the Part 1(OLE) of the study GA29145, this includes any 12-week safety follow-up data.

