4.2.3 Additional Safety Assessments

4.2.3.1 Laboratory Data

Selected laboratory parameters for safety reporting will be described further in the OLE population by summarizing the marked abnormalities and shift tables. Marked abnormalities will be identified according to a Sponsor-defined standard, which generally captures post-baseline laboratory values both outside a reference range and achieving a threshold percent change from baseline. Where needed, laboratory values will be linearly transformed to a standard reference range in order to account for intrinsic differences between males and females or measurement differences between laboratory standards.

Laboratory abnormalities and the patient's worst Common Terminology Criteria for Adverse Events (CTCAE) grade during study will be summarized for hematology and serum chemistry parameters, in addition to change from Baseline summaries.

Elevated liver enzyme tests will be summarized by the following upper limit of normal (ULN) categories as these are indicators of severe liver injury:

- ALT or AST > 3ULN and total bilirubin > 2 ULN as defined by Hy's law
- ALT or AST > 3 ULN

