4.2.3.3 ECGs

A shift table for the qualitative ECG assessments will be produced, summarizing the Baseline and worst post-baseline results.

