4.2.4 Open-Label Extension Timeframe

For the open-label extension population, the safety reporting timeframe is defined to capture safety information within the OLE treatment period only. It begins at first dose of study drug in Study GA29145 Part 1 (OLE). The end of the time-frame coincides with the last patient last visit, this includes safety follow-up in Study GA29145 Part 1 (OLE).

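### The baseline-dependent OLE safety outputs are measured from a parent-study value taken about 10 to 74 weeks before the first OLE dose, and no OLE-entry view is planned beside them

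*SAP*

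**What the plan says.** SAP 4.1.1 gives the only definition: "Baseline is defined as the last available assessment prior to first receipt of study drug in the Induction Phase of the parent study, GA29144". The same section defines OLE Day 1 as the day of the first OLE dose but does not make it a baseline for anything.

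The safety sections then rely on baseline without redefining it:

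- SAP 4.2.3.1: marked abnormalities generally capture "post-baseline laboratory values both outside a reference range and achieving a threshold percent change from baseline". Shift tables are planned, and laboratory abnormalities and worst CTCAE grade are given "in addition to change from Baseline summaries".
- SAP 4.2.3.2: vital signs are summarised as change from baseline, with clinically significant changes relative to baseline if appropriate.
- SAP 4.2.3.3: the ECG table is a shift table "summarizing the Baseline and worst post-baseline results".

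The reporting window is set elsewhere. SAP 4.2 starts safety data at the first dose in Part 1, and SAP 4.2.4 says that "the safety reporting timeframe is defined to capture safety information within the OLE treatment period only". SAP 4.2.2 ties treatment-emergence to the first OLE dose and counts an event already ongoing from GA29144 only if it worsens.

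**The concern.** The outputs that depend on a baseline use a reference point from one study and an observation window from the next. Adverse events carried over from GA29144 are filtered out unless they worsen. A carried-over laboratory, vital-sign or ECG shift has no such filter. The two halves of the safety report then describe different periods, although both appear in the single OLE Etrolizumab column and SAP 4.1.1 asks for tables by that group only.

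The incidence of laboratory abnormalities is a named safety outcome (SAP 1.3.2), and SAP 4 sends all safety outcomes into the CSR. Protocol 4.1.1 admits patients after disease worsening or clinical relapse as well as those who completed Maintenance, so their values at OLE entry may well differ from those at parent Week 0, in either direction.

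**Working it through.** The plan states no sample size, event rate or threshold for this point, so there is no figure to reproduce. The check is a comparison of the texts, an identity, and an illustration.

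**1. Length of the gap.** Protocol 4.1.2 excludes patients who leave GA29144 before Week 10, so the shortest gap from parent baseline to OLE entry is about 10 weeks. Protocol 4.1.1 admits Maintenance completers at Week 66 or Week 74, so the longest scheduled gap is about 74 weeks.

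**2. What a change from the parent baseline contains.** For any OLE measurement:

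OLE value − parent baseline = (OLE Day 1 value − parent baseline) + (OLE value − OLE Day 1 value)

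Only the second term arose within the window that SAP 4.2.4 sets. The first arose in GA29144, on placebo or on etrolizumab.

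**3. What a shift table shows.** Two patterns give the wrong impression of the OLE:

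- Normal at parent Week 0, abnormal at OLE Day 1, still abnormal in the OLE: normal to abnormal from the parent baseline, but abnormal to abnormal (no shift) from OLE Day 1.
- Abnormal at parent Week 0, normal at OLE Day 1, abnormal again in the OLE: abnormal to abnormal (no shift) from the parent baseline, but normal to abnormal from OLE Day 1.

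A third pattern is not misreported. If a value is abnormal at OLE Day 1 but normal at every measurement after the first OLE dose, nothing abnormal falls inside the window.

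**4. Which outputs depend on the baseline.** Dependent: the change leg of the marked-abnormality rule, laboratory and vital-sign change, and the laboratory and ECG shift tables. Not dependent: worst CTCAE grade, ALT or AST above 3 ULN, and the combined ALT/AST and bilirubin category (all SAP 4.2.3.1).

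**5. Whether OLE-entry values exist.** Protocol 4.4.4 states: "Data from the final visit of Study GA29144 will be used for analysis and data sets for the first visit of the OLE-SM study". Protocol Appendix 1 schedules haematology, chemistry, vital signs and ECG at Week 0, before dosing, and allows results from the final GA29144 visit to serve. No new collection is needed.

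**6. Illustration only.** Assume that a fraction p of patients became abnormal in GA29144 and stayed so, and that nothing changes in the OLE. With the stated maximum of 1150 patients, the apparent shifts number 1150 × p:

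- p = 2%: 23
- p = 5%: 57.5, about 58
- p = 10%: 115

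From an OLE Day 1 baseline the count is 0 in each case. The values of p are assumptions with no source in the documents, and 1150 is a ceiling for the whole OLE-SM study. The figures show how the effect scales and do not estimate it.

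**The case against.** The strongest reply is that the parent baseline is a deliberate and sound choice. The objective is long-term safety, many entrants had already received etrolizumab, and an OLE Day 1 baseline would absorb any change the drug had already caused. Parent Week 0 precedes all parent-study etrolizumab for every patient. This stands, and it is why the existing tables should stay.

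A reader might infer that OLE Week 0 is the true pre-etrolizumab value for anyone arriving on placebo. The documents do not support that. Protocol 1.3.3 describes placebo assignment in either the Induction or the Maintenance Phase, so a patient on Maintenance placebo may have had etrolizumab in Induction. The value at OLE entry is the latest pre-etrolizumab value only for patients who received placebo throughout GA29144. A pooled OLE Day 1 table would therefore mix pre-exposure and on-drug reference values, which is why a split by exposure is needed.

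The sponsor can also say that important new abnormalities reach the report by another route. Protocol 5.4.6.5 and 5.4.6.6 require laboratory and vital-sign findings to be reported as adverse events when they are symptomatic, change treatment, lead to intervention or are judged clinically significant, and those events are anchored to the first OLE dose. Worst CTCAE grade shows an abnormal OLE value whatever came before. Both points limit the consequence, but neither corrects the change and shift tables.

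Finally, the study is single-arm and descriptive, without tests, and is reported in a synoptic CSR. No decision rule depends on these tables. That also stands, and it sets the weight of the point.

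**Conclusion.** The mismatch holds as the SAP is written. The efficacy sections (SAP 4.1.3.1 to 4.1.3.3) restate the parent baseline explicitly; the safety sections do not, so it reaches them by default, and SAP 4.4 gives no reason. In the baseline-dependent safety outputs, a GA29144 change that persists or recurs is presented as OLE change, and OLE worsening back to the parent Week 0 level is hidden.

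Two stronger readings should be resisted. One is that all OLE laboratory safety results are affected: the outputs that use no baseline are not. The other is that every patient already shifted at OLE Day 1 is counted whatever happens next: the shift must be present at a measurement after the first OLE dose.

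The size cannot be derived from the documents, which give no share of patients with a shift at OLE entry. The thresholds for marked abnormalities sit in a Sponsor standard that is not part of them. The conclusion assumes that the general definition in SAP 4.1.1 applies wherever a safety section says baseline without qualification. It is a minor point, worth acting on because the remedy is cheap.

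**What to change.** Keep the parent-baseline tables as the cumulative view. For SAP 4.2.3.1 to 4.2.3.3:

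- Add change and shift tables, and the marked-abnormality summary, using the last value on or before the first OLE dose as the reference.
- Split the added tables by etrolizumab exposure in GA29144, any versus none.
- State in SAP 4.2.3 that post-baseline values are those after the first OLE dose. SAP 4.2 and 4.2.4 imply this, but the laboratory and ECG sections do not say it.
- Label each table with the baseline it uses.

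The cost is an additional set of safety tables in a synoptic CSR. The OLE-entry data are already scheduled or carried over from the final GA29144 visit; the split needs the parent-study treatment assignment.
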